**5.2 SAFETY PARAMETERS AND DEFINITIONS**

Safety assessments will consist of monitoring and recording adverse events, including serious adverse events and adverse events of special interest, performing protocol-specified safety laboratory assessments, measuring protocol-specified vital signs, and conducting other protocol-specified tests that are deemed critical to the safety evaluation of the study.

Patients will be evaluated for adverse events (all grades according to the NCI CTCAE v4.03), serious adverse events, and any adverse events requiring treatment interruption or discontinuation. Patients who have an ongoing adverse event leading to treatment discontinuation will be followed until the event resolves, the investigator assesses the event as stable, the patient is lost to follow-up, the patient undergoes HSCT, or the patient starts a different anti-tumor therapy.

Certain types of events require immediate reporting to the Sponsor, as outlined in Section [5.4](#).

### **5.2.1 Adverse Events**

According to the ICH guideline for Good Clinical Practice, an adverse event is any untoward medical occurrence in a clinical investigation subject administered a pharmaceutical product, regardless of causal attribution. An adverse event can therefore be any of the following:

- Any unfavorable and unintended sign (including an abnormal laboratory finding), symptom, or disease temporally associated with the use of a medicinal product, whether or not considered related to the medicinal product
- Any new disease or exacerbation of an existing disease (a worsening in the character, frequency, or severity of a known condition), except as described in Section [5.3.5.9](#)
- Recurrence of an intermittent medical condition (e.g., headache) not present at baseline
- Any deterioration in a laboratory value or other clinical test (e.g., ECG, X-ray) that is associated with symptoms or leads to a change in study treatment or concomitant treatment or discontinuation from study drug
- Adverse events that are related to a protocol-mandated intervention, including those that occur prior to assignment of study treatment (e.g., screening invasive procedures such as biopsies).

### **5.2.2 Serious Adverse Events (Immediately Reportable to the Sponsor)**

A serious adverse event is any adverse event that meets any of the following criteria:

- Fatal (i.e., the adverse event actually causes or leads to death)
- Life threatening (i.e., the adverse event, in the view of the investigator, places the patient at immediate risk of death)
- This does not include any adverse event that had it occurred in a more severe form or was allowed to continue might have caused death.
- Requires or prolongs inpatient hospitalization (Section [5.3.5.10](#))
- Results in persistent or significant disability/incapacity (i.e., the adverse event results in substantial disruption of the patient's ability to conduct normal life functions)
- Congenital anomaly/birth defect in a neonate/infant born to a mother exposed to study drug
- Significant medical event in the investigator's judgment (e.g., may jeopardize the patient or may require medical/surgical intervention to prevent one of the outcomes listed above)

The terms "severe" and "serious" are not synonymous. Severity refers to the intensity of an adverse event (e.g., rated as mild, moderate, or severe, or according to NCI CTCAE criteria; see Section [5.3.3](#)); the event itself may be of relatively minor medical significance (such as severe headache without any further findings).

Severity and seriousness need to be independently assessed for each adverse event recorded on the eCRF.

Serious adverse events are required to be reported by the investigator to the Sponsor immediately (i.e., no more than 24 hours after learning of the event; see Section 5.4.2 for reporting instructions).

### **5.2.3 Adverse Events of Special Interest (Immediately Reportable to the Sponsor)**

Adverse events of special interest are required to be reported by the investigator to the Sponsor immediately (i.e., no more than 24 hours after learning of the event; see Section 5.4.2 for reporting instructions). Adverse events of special interest for this study include the following:

- Cases of potential drug-induced liver injury that include an elevated ALT or AST in combination with either an elevated bilirubin or clinical jaundice, as defined by Hy's law (see Section 5.3.5.6)
- Suspected transmission of an infectious agent by the study drug, as defined below:

Any organism, virus, or infectious particle (e.g., prion protein transmitting transmissible spongiform encephalopathy), pathogenic or non-pathogenic, is considered an infectious agent. A transmission of an infectious agent may be suspected from clinical symptoms or laboratory findings that indicate an infection in a patient exposed to a medicinal product. This term applies only when a contamination of the study drug is suspected.
- TLS (clinical TLS per Howard criteria, see Appendix 13)
- Febrile neutropenia (Grade  $\geq 3$ )
- Thrombocytopenia (Grade  $\geq 3$  if associated with hemorrhage or bleeding)

*Reporting of this adverse event of special interest requires two separate forms: one form to report thrombocytopenia and one form to report hemorrhage/or bleeding.*
- Diarrhea (Grade  $\geq 2$ )
- Clostridium difficile infection (Grade  $\geq 2$ )

Note that patients with hematologic adverse events of special interest should be monitored with weekly blood counts until resolution. The final outcome must be reported in the eCRF. Hematological adverse events of special interest are not reportable for patients in whom myelosuppression arises as a result of confirmed relapsed disease.

## **5.3 METHODS AND TIMING FOR CAPTURING AND ASSESSING SAFETY PARAMETERS**

The investigator is responsible for ensuring that all adverse events (see Section 5.2.1 for definition) are recorded on the Adverse Event eCRF and reported to the Sponsor in accordance with instructions provided in this section and in Sections 5.4–5.6.

For each adverse event recorded on the Adverse Event eCRF, the investigator will make an assessment of seriousness (see Section 5.2.2 for seriousness criteria), severity (see Section 5.3.3), and causality (see Section 5.3.4).

### **5.3.1 Adverse Event Reporting Period**

Investigators will seek information on adverse events at each patient contact. All adverse events, whether reported by the patient or noted by study personnel, will be recorded in the patient’s medical record and on the Adverse Event eCRF.

**After informed consent has been obtained but prior to initiation of study drug**, only serious adverse events caused by a protocol-mandated intervention (e.g., invasive procedures such as biopsies, discontinuation of medications) should be reported (see Section 5.4.2 for instructions for reporting serious adverse events).

**After initiation of study drug until 56 days after the last dose of study drug**, all adverse events should be reported. Patients who, at 56 days after the last dose of study medication is administered, have an ongoing adverse event will be followed until the event resolves or the patient is lost to follow-up.

**After informed consent has been obtained until 6 months after the last dose of study medication is administered**, adverse events of special interest are reportable with the exception of hematological adverse events of special interest arising as a result of confirmed relapsed disease (see Section 5.2.3 for adverse event of special interest definition).

**After 56 days from the last dose of study drug until the end of the study**, the investigator should only report any serious adverse events that are believed to be related to the prior administration of study drug treatment or any fatal adverse events. Those should be reported on the eCRF Adverse Event page over the course of the study (see Section 5.6).

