## Follow-Up

Patients in CR/CRp/CRi after terminating study treatment will be followed for EFS, *DOR*, and *LFS*. HMRA will be performed monthly ( $\pm 5$  days) until disease progression/relapse is noted or until the patient moves to HSCT. Every 3 months HMRA will include assessment of bone marrow aspirate; in all other instances, HMRA will be based on peripheral blood counts only.

In the event of relapse, a HMRA based on a bone marrow aspirate is required. In addition, whole blood in EDTA for biomarker analysis should be obtained.

For patients who move to HSCT, an HMRA based on a bone marrow aspirate should be performed to document the bone marrow status prior to the start of conditioning therapy. The quantity of the bone marrow aspirate should also allow for exploratory biomarker analyses (MRD/Flow, EDTA, and Paxgene), and the hematopoietic cell transplantation-specific comorbidity index (HCT-CI) score (Sorrer et al. 2005; Sorror 2013) should be obtained to document the patient's health status prior to the start of conditioning therapy.

All patients will be followed every 3 months for study treatment-related serious adverse events, fatal adverse events, subsequent anti-cancer therapies, and survival status. Survival follow-up ends with death or end of study. Adverse events should be followed as outlined in Section 5.3.1 and Section 5.6. Please see [Appendix 1](#) for the schedule of follow-up assessments.

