## **5.6 POST-STUDY ADVERSE EVENTS**

The Sponsor should be notified if the investigator becomes aware of any serious adverse event that occurs after the end of the study, if the event is believed to be related to the prior study medication.

Adverse events of special interest are reportable until 6 months after the last dose of study medication is administered, with the exception of hematological adverse events of special interest arising as a result of confirmed relapsed disease (refer to Section [5.2.3](#) for adverse events of special interest definitions).

The investigator should report these events directly to Roche Safety Risk Management either by faxing or by scanning and emailing the Serious Adverse Event/ Adverse Event of Special Interest Reporting Form using the fax number or email address provided by the Sponsor.

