##### **4.7.2 Adverse Events**

Coding of adverse events will be done using the most recent version of the Medical Dictionary for Regulatory Activities (MedDRA). All adverse events and

laboratory parameters will be assessed according to the National Cancer Institute Common Terminology Criteria for Adverse Event (NCI CTCAE) version 4.03 grading system.

All adverse events will be reported from the day of first study treatment. All adverse events will be displayed by body system (system organ class), NCI CTCAE grade, and relation to study treatment. All serious adverse events, Grade  $\geq 3$  adverse events, adverse events leading to death, adverse events leading to study treatment modification, adverse events leading to study treatment discontinuations, and adverse events leading to early study withdrawals will be summarized by treatment arm.

Deaths and reason for deaths reported during the study will be summarized by treatment arm. Deaths occurring within 30 and 60 days after randomization will also be summarized.

In the summary tables showing the overall incidence of adverse events, patients who experienced the same event on more than one occasion will be counted only once in the calculation of the event frequency. The adverse event with the most extreme intensity will be used for reporting.

Additional analyses will be performed by treatment arm based on the selected adverse events of special interest, which are defined in the study protocol, as well as based on any adverse event, which might require further investigation. Analyses of the time to onset of these adverse events will be performed. Time to adverse events will be listed. Patients without an adverse event will be censored at last date known to be alive.

In order to account for potential differences in the duration of adverse event reporting between treatment groups, an exploratory analysis of selected adverse events by duration of exposure might be performed based on adverse event rates adjusted for patient-years at risk when enough events are observed.

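### SAP 4.7.2 does not separate adverse events that follow the next anti-leukaemic therapy or transplant, and it censors time to onset after event collection has closed

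*Protocol*

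**What the plan says.** Protocol 5.3.1 sets overlapping collection periods. The general one runs "After initiation of study drug until 56 days after the last dose of study drug" and covers every AE. For AESIs the period extends to 6 months after the last dose, and within it "adverse events of special interest are reportable with the exception of hematological adverse events of special interest arising as a result of confirmed relapsed disease". Section 5.6 repeats the limit: "Adverse events of special interest are reportable until 6 months after the last dose of study medication is administered". Under 5.3.1 and 5.4.2.2, related serious AEs and all fatal AEs are reported until the end of the study. None of these periods ends at a new anti-leukaemic therapy or HSCT. By contrast, 5.2 stops following an ongoing AE that led to discontinuation if, among other things, "the patient undergoes HSCT, or the patient starts a different anti-tumor therapy".

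Two other places describe narrower collection. The Follow-Up text in 4.5.2 says "All patients will be followed every 3 months for study treatment-related serious adverse events, fatal adverse events, subsequent anti-cancer therapies, and survival status" and does not mention AESIs. Footnote e to Appendix 1 Table 3 restricts collection to related serious AEs and fatal AEs. As the table was extracted, it covers patients after treatment failure, relapse or HSCT. The column alignment should be confirmed in the original.

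On analysis, SAP 4.7.2 gives a start, "All adverse events will be reported from the day of first study treatment", but no end and no rule for later therapy. It adds that "Additional analyses will be performed by treatment arm based on the selected adverse events of special interest", with time-to-onset analyses censored at the date last known alive. It shows AEs by relation to study treatment, counts each patient once per event, and makes rates per patient-year optional. SAP 4.1.4 and protocol 6.6 analyse safety by treatment received.

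**The concern.** Dosing lasts five days, induction is normally one cycle, and treatment failure ends study drug. Many patients could therefore start another therapy while AEs, and especially AESIs, are still being collected. The AESI list includes febrile neutropenia, thrombocytopenia with bleeding, diarrhoea and *C. difficile* infection. These are not specific to idasanutlin. Section 1.3 of the protocol lists marrow suppression and diarrhoea for cytarabine, and most salvage regimens in Appendix 16 contain cytarabine.

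The trial is designed on the expectation that response differs by arm, so the type and timing of the next therapy may differ too. The by-arm AE, AESI and fatal-AE tables would then mix study-drug toxicity with toxicity of what followed. Efficacy has a counterpart to this problem: SAP 4.4.3 repeats OS with censoring at new treatment and at HSCT. Safety has none.

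The censoring rule is a separate fault. A patient cannot be observed to have a routinely reportable event after reporting has closed, yet stays in the risk set.

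**Working it through.** **1. The rules side by side**

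| Item | Collection ends (protocol 5.3.1, 5.4.2.2, 5.6) | Analysis ends (SAP 4.7.2) |
|---|---|---|
| All AEs | 56 days after last dose | not stated |
| AESIs | 6 months after last dose | not stated |
| Related serious AEs, fatal AEs | end of study | not stated |
| Time to onset, no event | as above | last date known alive |

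Neither column refers to new therapy or HSCT.

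**2. When collection closes.** With one cycle the last dose is on Day 5. General AE collection then closes on Day 5 + 56 = 61, and AESI collection on Day 5 + 183 = 188. With three 28-day cycles the last dose is on Day 2 × 28 + 5 = 61, so the dates are Day 117 and Day 244. If Cycles 1 and 2 each run to the permitted 56 days, the last dose is on Day 2 × 56 + 5 = 117, and the dates are Day 173 and Day 300. Closing dates thus differ by 56 to 112 days between one-cycle and three-cycle patients. A one-cycle patient alive on Day 365 and free of an AESI contributes 365 − 188 = 177 days at risk with no routine AESI collection.

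**3. Share of each window under the next therapy.** Assume it starts between Day 30 and Day 45 after one cycle; the documents give no start date.
- General window: (61 − 45)/56 = 29% to (61 − 30)/56 = 55%.
- AESI window: (188 − 45)/183 = 78% to (188 − 30)/183 = 86%.

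**4. Planned difference in response.** Protocol 6.1 assumes CR of 0.16 (control) and 0.323 (idasanutlin). The odds ratio is (0.323/0.677)/(0.16/0.84) = 2.505, which reproduces the stated 2.5. Non-CR is 84% against 67.7%, a gap of 16.3 points.

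**5. Possible effect on crude incidence.** As a rough model, treat non-CR patients as candidates for salvage (uptake s, event risk fs) and CR patients as candidates for HSCT (uptake t, event risk ft). Added difference, idasanutlin minus control = 16.3 × (t·ft − s·fs) points. Assume uptake of 30–70% and event risk of 40–80%, so each product lies between 0.12 and 0.56.
- Salvage alone: −16.3 × 0.12 = −2.0 to −16.3 × 0.56 = −9.1 points.
- Both: ±16.3 × (0.56 − 0.12) = ±7.2 points, and zero when the products are equal.
- If 60% already had the event and are counted once, both together: 0.4 × 7.2 = ±2.9 points.

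**6. A worked AESI.** Observed risk = 1 − (1 − p)(1 − q), where q = (1 − CR)·s·f + CR·h·g; f is the salvage event risk, and h and g are HSCT uptake and event risk. Take true risks of 40% (control) and 50% (idasanutlin), and s·f from 0.20 to 0.56.
- Salvage only: the 10-point gap becomes 56.8 − 50.1 = 6.7 to 69.0 − 68.2 = 0.7 points.
- With h·g = 0.5 × 0.8 = 0.4: 9.3 to 3.4 points.
- No drug effect (45% each): 0.55 × 16.3 × (h·g − s·f) gives −5.0 (s·f = 0.56, no HSCT) to +1.8 points (s·f = 0.20, h·g = 0.4).

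Part of the shrinkage is plain dilution. Giving both arms the same q, taken from either arm, leaves 10 × (1 − q) = 8.3–8.6 points in the mild salvage-only case and 5.3–6.2 in the extreme one. That accounts for roughly 40–50% of the loss.

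**The case against.** The other side has several good points.

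- **Attribution.** A reader might infer that events are charged to the randomised arm. They are not: safety is analysed by treatment received, though the two coincide for most patients.
- **Relatedness.** AEs are shown by relation to study treatment, and blinded investigators are told to weigh alternative causes (protocol 5.3.4). This is a real mitigation. It is limited because the toxicities overlap and because SAP 4.10 counts a missing relationship as related.
- **Actual collection.** If sites follow Appendix 1 footnote e, less later toxicity reaches the database. The documents conflict, so the amount captured cannot be known from them. This argues for reconciliation.
- **Salvage pool.** A reader might take 84% and 67.7% as the patients heading for salvage. The documents do not support that. Under protocol 4.5.8, CRp and CRi are not treatment failure; a good PR may have a second induction cycle (4.3.2.3); and early deaths receive no further therapy. No planning rates for CRp or CRi are given.
- **Truncation.** Cutting the main tables at the next therapy would shorten observation, possibly more in one arm, and would move late fatal AEs out of view. This stands. It rules out replacing the full-window tables.

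None of these points supplies an analysis that separates later events by timing, and none defends the censoring date.

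**Conclusion.** The gap is in the text and needs no assumption: collection runs past the next therapy, the SAP has no timing rule to separate those events, and time to onset is censored later than routine collection closes. Because closing depends on the last dose, the mismatch varies with the number of cycles and may differ by arm.

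That the comparison *can* be distorted follows. That it *is* distorted, or in a known direction, does not. Salvage toxicity may load one arm and transplant toxicity the other, and they may cancel. The ranges above (−7.2 to +7.2 points, or about ±2.9 when most patients already had the event) rest on assumed uptake, risks and start dates and on a simplified pool, so they show scale only. The concern is with interpretation of safety, not the primary OS test.

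**What to change.** In SAP 4.7.2:

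1. Censor time to AE or AESI onset at the earliest of: death or last contact; the end of the applicable window (56 days, or 6 months for AESIs); and the start of new anti-leukaemic therapy or HSCT. Use the transplant date if the start of conditioning is not collected; protocol 4.5.3 lists the transplant date and conditioning type only.
2. Keep the full-window tables. Add by-arm AE, serious AE, AESI and fatal-AE tables limited to events before new anti-leukaemic therapy or HSCT, and show later events separately. Give exposure-adjusted rates alongside, because truncation may differ by arm.
3. Reconcile protocol 5.3.1 with Appendix 1 Table 3 footnote e, so that what is collected after failure, relapse or HSCT is unambiguous.

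The cost is SAP wording and a few extra tables. Subsequent therapies and transplant dates are already collected. The downside is that delayed drug effects emerging after the next therapy appear only in the full-window and later-event tables.

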### **5.3.2 Eliciting Adverse Event Information**

A consistent methodology of non-directive questioning should be adopted for eliciting adverse event information at all patient evaluation timepoints. Examples of non-directive questions include the following:

“How have you felt since your last visit to the clinic?”

“Have you had any new or changed health problems since you were last here?”

### 5.3.3 Assessment of Severity of Adverse Events

The adverse event severity grading scale for the NCI CTCAE v4.03 will be used for assessing adverse event severity. [Table 5](#) will be used for assessing severity for adverse events that are not specifically listed in the NCI CTCAE.

**Table 5 Adverse Event Severity Grading Scale for Events Not Specifically Listed in NCI CTCAE**

Grade	Severity
1	Mild; asymptomatic or mild symptoms; clinical or diagnostic observations only; or intervention not indicated
2	Moderate; minimal, local, or non-invasive intervention indicated; or limiting age-appropriate instrumental activities of daily living a
3	Severe or medically significant, but not immediately life-threatening; hospitalization or prolongation of hospitalization indicated; disabling; or limiting self-care activities of daily living b,c
4	Life-threatening consequences or urgent intervention indicated d
5	Death related to adverse event d

CTCAE= Common Terminology Criteria for Adverse Events; NCI= National Cancer Institute.

Note: Based on the most recent version of NCI CTCAE v4.03, which can be found at: [http://ctep.cancer.gov/protocolDevelopment/electronic\\_applications/ctc.htm](http://ctep.cancer.gov/protocolDevelopment/electronic_applications/ctc.htm)

- a Instrumental activities of daily living refer to preparing meals, shopping for groceries or clothes, using the telephone, managing money, etc.
- b Examples of self-care activities of daily living include bathing, dressing and undressing, feeding oneself, using the toilet, and taking medications, as performed by patients who are not bedridden.
- c If an event is assessed as a “significant medical event,” it must be reported as a serious adverse event (see Section 5.4.2 for reporting instructions), per the definition of serious adverse event in Section 5.2.2.
- d Grade 4 and 5 events must be reported as serious adverse events (see Section 5.4.2 for reporting instructions), per the definition of serious adverse event in Section 5.2.2.

